Study title: Plastic stents vs fully covered self expanding metal stents (FCSEMS) for treatment of anastomotic bile leaks following orthotopic liver transplant: a randomized controlled trial

Principal Investigator: [name] MPH

Revision Date: October 11, 2017

Background:

Orthotopic liver transplant (OLT) can be a life-saving intervention for patients with decompensated liver disease. Typical surgical biliary reconstruction at the time of OLT is creation of an anastomosis between the donor common hepatic duct and recipient bile duct. Bile leaks arising from this anastomosis early in the post-transplant period are a known potential adverse event of OLT and may result in significant morbidity including intra-abdominal infection, need for repeat liver transplant, and death.

Standard endoscopic management for anastomotic bile leaks following OLT has been endoscopic retrograde cholangiopancreatography (ERCP) with placement of a temporary plastic biliary endoprosthesis (stent) across the site of anastomotic leak. While this intervention carries a high rate of technical success, clinical success is not universal. In a retrospective study of patients undergoing ERCP for post-OLT anastomotic bile leak at VUMC between 2009 and 2014, ERCP with placement of a plastic stent resulted in resolution of bile leak in 60% of patients. The remaining 40% of patients experienced refractory anastomotic bile leaks. Patients with refractory anastomotic leaks were found to be at increased risk of surgical re-intervention, repeat transplant, and death [1].

An alternative to placement of a plastic biliary stent is placement of a fully covered self-expanding metal stent (FCSEMS). FCSEMS have been granted United States Food & Drug Administration approval for categories of both malignant and benign bile duct disease. Whereas a plastic stent functions largely as a wick to siphon bile flow, the theoretical advantage of a FCSEMS is that the relatively larger expansile diameter and membrane coating provide an actual and effective seal at the site of leak. FCSEMS have been used successfully for salvage therapy of anastomotic bile leaks in the post-OLT population at VUMC [1], with no serious stent related adverse events and no cases of unsuccessful FCSEMS removal in this population.

The objective of this study is to prospectively randomize patients found to have anastomotic bile leaks following OLT to placement of either a plastic biliary stent or a FCSEMS at initial ERCP intervention.

Study hypothesis:

Placement of FCSEMS as initial treatment for anastomotic bile leak following OLT will result in a higher rate of leak resolution compared to placement of a plastic stent.

Study endpoints/outcome measures:

Primary endpoint:

Cholangiographic resolution of bile leak at follow-up ERCP 6 weeks following placement of a plastic stent or FCSEMS.

Secondary endpoints:

Study title: Plastic stents vs fully covered self expanding metal stents (FCSEMS) for treatment of anastomotic bile leaks following orthotopic liver transplant: a randomized controlled trial

Principal Investigator: [name] MPH

Revision Date: October 11, 2017

- 1) Need for repeat endoscopic intervention (ERCP) within initial 8 weeks following placement of a plastic stent or FCSEMS
- 2) Need for percutaneous drainage of biloma or intraabdominal fluid collection following placement of a plastic stent or FCSEMS
- 3) Need for surgical biliary reconstruction for refractory anastomotic bile leak
- 4) Need for repeat OLT
- 5) Death at 90 days
- 6) Rate of post-ERCP pancreatitis (PEP) following placement of a plastic stent vs FCSEMS
- 7) Rate of stent migration following placement of a plastic stent vs FCSEMS
- 8) Rate of anastomotic biliary stricture at follow-up ERCP 8 weeks following placement of a plastic stent or FCSEMS
- 9) Need for repeat ERCP for management of anastomotic biliary stricture within 90 days following leak resolution

Methods:

Eligibility: All adult patients undergoing ERCP for suspected anastomotic bile leak within 60 days following OLT with standard biliary reconstruction will be eligible for study participation. Clinical decision to proceed with ERCP will be at the discretion of the liver transplant service when a bile leak is suspected on the basis of bilious percutaneous drain output, imaging findings, or other clinical criteria.

Cognitively impaired population is eligible if surrogate has legal power of attorney.

Patients who have undergone OLT with hepaticojejunostomy will not be eligible for participation.

Patients who have undergone percutaneous transhepatic cholangiogram with percutaneous biliary intervention following OLT and prior to ERCP will not be eligible for participation.

Study intervention: Potential subjects will be consented prior to ERCP. ERCP will be performed in standard fashion. If cholangiogram demonstrates a high-grade anastomotic bile leak (evident without occlusion cholangiogram) and successful transpapillary wire access across the leak is established, subject randomization will then take place. Study allocation to plastic stent vs FCSEMS will be determined by the contents of a sealed envelope. Patients randomized to plastic stents will receive a 10 French stent, with stent length sufficient to traverse both the anastomosis and papilla selected at the discretion of the endoscopist. Patients randomized to FCSEMS will receive an 8 mm diameter by 80 mm length Wallflex (Boston Scientific) FCSEMS. Consistent with current endoscopic practice among this population, biliary sphincterotomy will be performed prior to stent placement unless prohibited by coagulopathy and/or thrombocytopenia.

The study consists of a one-time intervention, randomization to plastic vs metal stent, during procedure while patient is under anesthesia. There is no further study intervention, and all subsequent clinical interactions and procedures (if necessary) will be performed as part of standard (non-study) clinical care. It is not expected that subjects will lose capacity or ability to withdraw consent. However, if a

Study title: Plastic stents vs fully covered self expanding metal stents (FCSEMS) for treatment of anastomotic bile leaks following orthotopic liver transplant: a randomized controlled trial

Principal Investigator: [name] MPH

Revision Date: October 11, 2017

subject is identified as incapable of consenting on his/her own behalf, the individual authorized to provide consent for ERCP procedure will be identified as the individual authorized to provide consent for study participation. That person must provide a legal power of attorney document.

Study follow-up: All patients will be assessed by the gastroenterology consult service on post-operative day 1 following ERCP for the presence of post-procedure adverse events, as is typical practice.

Patients will be scheduled for follow-up ERCP for stent removal at 6 weeks following initial placement of a plastic stent or FCSEMS. Repeat ERCP may be performed sooner than 6 weeks at the discretion of the transplant team if there is clinical suspicion for refractory bile leak following initial stent placement.

Adjudication of the primary study endpoint will be determined by the presence/absence of persistent anastomotic bile leak at first follow-up ERCP after initial stent placement, whether performed at 6 weeks or sooner.

Study participation for all subjects will be complete at this point in time, with continued standard care as directed by the transplant team. Additional secondary outcomes will be assessed by longitudinal follow-up during a 90-day period following initial stent placement.

Power calculation and statistical analysis plan: Statistical comparison of the primary study outcome, proportion of patients with refractory bile leak, will be performed using Chi-square statistic. Prior data indicate that the refractory anastomotic bile leak rate following placement of a plastic biliary stent is 40% [1]. Assuming that the refractory leak rate following placement of a FCSEMS is 10%, this study would need to enroll 32 subjects in the plastic stent arm and 32 subjects in the FCSEMS arm to be able to reject the null hypothesis that the refractory leak rate for plastic vs FCSEMS is the same with 80% power and a Type I error rate of 0.05.

Study timeline: Assuming an annual OLT volume of 150 patients at VUMC, and assuming 10% of OLT recipients will experience an anastomotic bile leak, we expect to enroll to study target (64) patients within a 4 to 5 year time frame.

Study funding: The study will not be supported or funded by industry, and the collection, analysis, interpretation, and publication of data will be independent of industry.

Reference:

Study title: Plastic stents vs fully covered self expanding metal stents (FCSEMS) for treatment of anastomotic bile leaks following orthotopic liver transplant: a randomized controlled trial

Principal Investigator: [name] MPH

Revision Date: October 11, 2017

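### Secondary endpoint 8 reads stricture at an 8-week ERCP, but the only scheduled follow-up ERCP is the stent removal at 6 weeks

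*Combined protocol and SAP*

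**What the plan says.** Under Study endpoints/outcome measures, secondary endpoint 8 is "Rate of anastomotic biliary stricture at follow-up ERCP 8 weeks following placement of a plastic stent or FCSEMS". The primary endpoint in the same section has the same construction with a different number: "Cholangiographic resolution of bile leak at follow-up ERCP 6 weeks following placement of a plastic stent or FCSEMS".

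The schedule is in Methods, Study follow-up: "Patients will be scheduled for follow-up ERCP for stent removal at 6 weeks following initial placement of a plastic stent or FCSEMS". The one stated departure is towards an earlier date: "Repeat ERCP may be performed sooner than 6 weeks at the discretion of the transplant team", on clinical suspicion of a refractory leak. The primary endpoint is then adjudicated at the "first follow-up ERCP after initial stent placement, whether performed at 6 weeks or sooner".

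The Study intervention section says of everything after the randomised stent placement that "all subsequent clinical interactions and procedures (if necessary) will be performed as part of standard (non-study) clinical care". The text after the adjudication rule ends study participation at that first follow-up ERCP. It then says that further secondary outcomes are collected over the 90 days after the first stent was placed.

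**The concern.** An endpoint read on a cholangiogram needs a cholangiogram. Endpoint 8 places its reading at week 8, and the protocol plans no ERCP for that week. If the definition is followed as written, stricture is known only for patients who return to ERCP around week 8 for a clinical reason. That group is selected after randomisation, and the selection may differ by arm, so the result would not be the stricture rate in either randomised group.

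The practical risk is two defensible denominators. One person extracting data could use the 6-week cholangiogram for nearly everyone. Another could look for a standard-care ERCP near week 8 and use only those patients. The protocol does not choose between them, and a choice made once the data are visible would be post hoc.

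**Working it through.** **1. The plan's own figure.** The stated sample size is 32 per arm, from refractory-leak rates of 40% and 10%, 80% power and a type I error of 0.05 (sidedness is not stated; two-sided assumed). With the pooled-variance two-proportion formula and a mean rate of 0.25:

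n = [1.960 × √(2 × 0.25 × 0.75) + 0.842 × √(0.40 × 0.60 + 0.10 × 0.90)]² / 0.30²

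n = [1.200 + 0.483]² / 0.09 = 31.5, rounded up to 32 per arm (64 in total). Power at 32 per arm is 80.6%. The figure reproduces, and no term in it involves endpoint 8.

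**2. Timings side by side.**

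| Item | Section | Time after placement |
|---|---|---|
| Scheduled follow-up ERCP (stent removal) | Study follow-up | 6 weeks = day 42 |
| Permitted departure | Study follow-up | earlier than day 42 |
| Primary endpoint reading | Study endpoints; Study follow-up | first follow-up ERCP, day 42 or sooner |
| Endpoint 8 reading | Study endpoints | 8 weeks = day 56 |
| Collection of secondary outcomes | after the adjudication rule | to day 90 |

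The gap between the endpoint 8 time and the scheduled ERCP is 56 − 42 = 14 days. Day 56 lies inside the 90-day collection period, so an ERCP done then could be recorded, but none is scheduled. The number of patients with an ERCP scheduled at week 8 is 0 of 32 + 32 = 64.

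**3. What the literal definition would yield.** The only possible source is an ERCP done near day 56 as standard care. The documents give no rate for such procedures and no stricture rate, so neither the size of that subset nor any bias can be calculated, and none is claimed.

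**4. What the correction does to timing.** Reading stricture at the first follow-up ERCP means that some patients are read before day 42. Suspected refractory leak is the stated trigger for an early ERCP, and the plan assumes refractory leak in 40% against 10%. Let f be the share of those leaks that prompts an early ERCP. The documents do not give f, so its full range is shown:

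- Plastic: f × 0.40 × 32 = 12.8f
- FCSEMS: f × 0.10 × 32 = 3.2f

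| f (assumed) | Plastic, read early | FCSEMS, read early |
|---|---|---|
| 0 | 0 | 0 |
| 0.5 | 6.4 | 1.6 |
| 1 | 12.8 | 3.2 |

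These counts leave out early ERCPs prompted by a suspicion that proves wrong. They illustrate the possible imbalance and do not predict it.

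**The case against.** The best case on the other side is that this is a one-number slip. The protocol uses the term follow-up ERCP for the stent removal and for the procedure that decides the primary endpoint, and endpoint 8 uses the same term. On that reading the stricture assessment is available at the planned removal, the selected-subset problem never arises, and only an unpowered secondary endpoint needs a corrected number.

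Much of this stands: the 6-week ERCP was probably meant. But the text does not settle it. The rule about the first follow-up ERCP is written only for the primary endpoint, other secondary outcomes are assigned to 90-day follow-up, no visit window ties week 8 to week 6, and 8 weeks also appears in endpoint 1, so the figure is not plainly an isolated slip.

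Two stronger readings are tempting, and the documents support neither.

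- *Data collection has stopped by week 8.* A reader might infer this from the end of participation at the first follow-up ERCP. The next sentence of the protocol continues collection of secondary outcomes to day 90. What is missing at week 8 is a scheduled ERCP, not follow-up.
- *Endpoint 1 is defective too.* It is worded "Need for repeat endoscopic intervention (ERCP) within initial 8 weeks following placement of a plastic stent or FCSEMS", and the planned removal falls inside that window, so a reader might infer that nearly every patient would count as an event. The wording is about need. Study follow-up uses *repeat* for early ERCPs on suspicion of leak and *follow-up* for the scheduled removal. Endpoint 9 likewise speaks of "Need for repeat ERCP for management of anastomotic biliary stricture within 90 days following leak resolution". All of this points to clinically driven procedures, so endpoint 1 does not need to change.

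**Conclusion.** The assessment time stated for endpoint 8 conflicts with the protocol's own schedule and should be corrected. As written, 0 of 64 patients have a planned assessment at that time, which is 14 days after the only scheduled ERCP. This rests on the text alone and needs no assumed rate. The harm depends on the literal reading being followed: a stricture result from a clinically selected subset, with a denominator the protocol does not fix. If the analyst uses the 6-week ERCP, as was probably intended, that harm does not occur.

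The point is confined to one secondary endpoint. It does not touch the primary endpoint, the sample size of 64 or the power, and it does not show that any stricture result would be biased in a particular direction or by a particular amount.

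**What to change.** Redefine endpoint 8 as anastomotic biliary stricture at the first follow-up ERCP, planned at 6 weeks or done sooner, which is the same procedure that decides the primary endpoint. For each arm, report the timing of that ERCP and the numbers of patients assessed and not assessed. Do not count unassessed patients as free of stricture.

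The cost is a reworded endpoint and a reporting line. No visit or procedure is added, because the primary endpoint already needs that cholangiogram. The drawback is the one sized above: if early ERCPs are more frequent in one arm, stricture is read at different times in the two arms. Reporting the timing by arm shows this but does not remove it.

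### As written, a leak that closes after percutaneous transhepatic biliary rescue is scored as resolved at the first follow-up ERCP, and no endpoint records the rescue

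*Combined protocol and SAP*

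**What the plan says.** The primary endpoint, under Study endpoints/outcome measures, is "Cholangiographic resolution of bile leak at follow-up ERCP 6 weeks following placement of a plastic stent or FCSEMS". Methods, Study follow-up, gives the operational rule: the endpoint is "determined by the presence/absence of persistent anastomotic bile leak at first follow-up ERCP after initial stent placement", at 6 weeks or earlier. The power section names the same outcome as the proportion with refractory leak.

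On care after the index procedure, Methods, Study intervention, says: "There is no further study intervention, and all subsequent clinical interactions and procedures (if necessary) will be performed as part of standard (non-study) clinical care". Study follow-up allows an ERCP before 6 weeks, at the transplant team's discretion, when a refractory leak is suspected.

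Percutaneous transhepatic biliary intervention is named once, as an exclusion under Eligibility: "Patients who have undergone percutaneous transhepatic cholangiogram with percutaneous biliary intervention following OLT and prior to ERCP will not be eligible for participation".

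The secondary endpoints that could pick up a rescue are:
- Endpoint 1: "Need for repeat endoscopic intervention (ERCP) within initial 8 weeks following placement of a plastic stent or FCSEMS"
- Endpoint 2: "Need for percutaneous drainage of biloma or intraabdominal fluid collection following placement of a plastic stent or FCSEMS"
- Endpoint 3: "Need for surgical biliary reconstruction for refractory anastomotic bile leak"
- Endpoint 4: repeat transplant

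Endpoints 5 to 9 cover death, pancreatitis, stent migration, stricture and ERCP for stricture.

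**The concern.** Before the index ERCP, the protocol treats transhepatic biliary intervention as important enough to disqualify a patient. After randomisation it is open to standard care, and nothing says how it enters the analysis. Suppose a stent does not control the leak, the patient has a transhepatic intervention for it, and the leak is absent at the first follow-up ERCP. The rule then gives the same result as for a patient whose stent worked unaided.

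The study hypothesis concerns leak resolution after the initial stent. Each such patient moves from failure to success in the primary comparison. With only about 16 failures expected in the whole trial on the plan's own rates, a few reclassified patients matter. Because the procedure is not an endpoint, the planned tables would not show how often this happened or in which arm.

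**Working it through.** **Step 1. Does any text handle the rescue?** Set side by side, the endpoint definition and the adjudication rule both look only at the cholangiogram, and neither has an exception. The Study intervention section leaves later procedures open. Endpoint 1 counts ERCP, endpoint 2 drainage of a biloma or fluid collection, endpoint 3 surgery and endpoint 4 retransplant. Endpoint 2 comes closest, but draining a collection is not the same as entering the biliary tree through the liver, and the Eligibility section names the latter as a procedure of its own. No text counts the rescue as failure, censors it or reports it.

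**Step 2. Which patients are affected?**
- ERCP before the rescue: the leak is seen and scored as refractory. Correct.
- Rescue first, then a first follow-up ERCP with no leak: scored as resolved. This is the gap.
- Rescue and no follow-up ERCP: the outcome is missing. That is a separate matter.

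**Step 3. Reproduce the plan's sample size.** Inputs from the power section: 40% vs 10% refractory, 80% power, alpha 0.05 (two-sided assumed; the plan does not say), chi-square test. With pooled variance and no continuity correction, the mean rate is (0.40 + 0.10)/2 = 0.25 and

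n = [1.960 × √(2 × 0.25 × 0.75) + 0.842 × √(0.40 × 0.60 + 0.10 × 0.90)]² / 0.30² ≈ 31.5, rounded up to 32 per arm.

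This matches the plan. Power at 32 per arm is 80.6% by the normal approximation. Exact enumeration of two binomials with the uncorrected chi-square test gives 82.8%, and that exact method is used below.

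**Step 4. Size of the effect under an assumed rescue share.** Let r be the share of true failures that are rescued and leak-free at the first follow-up ERCP. The documents do not give r. With the same r in both arms, the recorded rates are 0.40(1 − r) and 0.10(1 − r), and the expected number reclassified is 32 × (0.40 + 0.10) × r = 16r.

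| r (assumed) | Recorded rates | Patients reclassified, whole trial | Exact power, 32 per arm |
|---|---|---|---|
| 0 | 40% vs 10% | 0 | 82.8% |
| 5% | 38% vs 9.5% | 0.8 | 80.0% |
| 10% | 36% vs 9% | 1.6 | 77.0% |
| 12.5% | 35% vs 8.75% | 2.0 | 75.4% |
| 25% | 30% vs 7.5% | 4.0 | 66.8% |

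**Step 5. Unequal use.** The plan's difference is 30 points. If r = 25% in the plastic arm only, the recorded rates are 30% vs 10%, a difference of 20 points. If r = 25% in the FCSEMS arm only, they are 40% vs 7.5%, a difference of 32.5 points. The bias can run either way.

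**The case against.** The protocol's stated route for a suspected refractory leak is an earlier ERCP, and the first follow-up ERCP decides the endpoint. A failure examined that way is scored correctly whatever follows. Every randomised patient had successful wire access across the leak, so endoscopic re-access is plausible. Misclassification needs a chain: failure, transhepatic rescue without a prior ERCP, a later ERCP, and closure by then. The Background lists surgical re-intervention, repeat transplant and death after refractory leak, and FCSEMS as salvage; it does not mention transhepatic rescue. All this stands and limits the likely size. It does not close the gap, because the early ERCP is discretionary.

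It can also be argued that cholangiographic state at follow-up, whatever care came in between, is a legitimate target for comparing initial-stent strategies. That is fair, but the plan does not state this choice, and it calls the outcome refractory leak.

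A reader might infer that the rule is simply wrong, that such failures leave no trace, or that the trial is underpowered because of it. The documents do not support those readings. The rule is silent rather than mistaken, and the same patient may still appear under endpoint 1 through an early ERCP or under endpoint 2 through drainage of a collection. At r = 5%, power is still 80.0%.

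Lastly, counting rescue as failure brings a clinician's decision into an endpoint now read from a cholangiogram, and the protocol describes no blinding. A lower threshold for intervening in one arm would create failures there. This stands as a real downside.

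**Conclusion.** The gap holds on the text: the rule scores a leak that closed after transhepatic rescue as resolved, and no secondary endpoint records that procedure. How often this happens is not known from the documents. With equal rescue shares, the loss runs from nothing to about 16 points of power at r = 25% (82.8 − 66.8 = 16.0). These figures assume the plan's 40% and 10%, 32 per arm, an uncorrected two-sided chi-square test, and that every rescued patient counted in r is scored as resolved. With unequal use, the direction cannot be predicted.

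A reader might infer a bias toward no difference because the plastic arm is expected to have more failures. That follows only if rescue is about equally common per failure or commoner after plastic stents, and the documents say neither. This is a cheap improvement worth making, not a flaw shown to threaten the result.

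**What to change.** 1. Add to the adjudication rule under Study follow-up: *A patient who has a percutaneous transhepatic biliary intervention with recorded indication of persistent anastomotic bile leak, between randomisation and the first follow-up ERCP, is counted as having a refractory leak.*
2. Report the cholangiogram-only classification as a sensitivity analysis.
3. Extend secondary endpoint 2 to include percutaneous transhepatic biliary intervention after stent placement, reported by arm.

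Cost: a few sentences, using procedures and indications expected in the hospital record. The sample size stands, provided the assumed 40% and 10% already count rescued patients as failures. Clinical care is not altered. The downside is that the rule admits a clinical decision made without described blinding and relies on the recorded indication to separate leak from other reasons. The sensitivity analysis makes visible how much the result depends on it.

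### Is it an error that the primary chi-square test makes no use of hepatic artery disease, which the title of the plan's only reference links to refractory leak?

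*Combined protocol and SAP*

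**What the plan says.** All references are to the combined protocol and SAP.

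- *Power calculation and statistical analysis plan* sets out the primary test in one sentence: "Statistical comparison of the primary study outcome, proportion of patients with refractory bile leak, will be performed using Chi-square statistic". No covariate or stratum is named. The section assumes refractory leak in 40% of plastic-stent patients and 10% of FCSEMS patients, with 32 per arm, 80% power and a type I error of 0.05. The 40% is taken from reference 1.
- *Study intervention*: "Study allocation to plastic stent vs FCSEMS will be determined by the contents of a sealed envelope". No stratification factor is named.
- *Reference*: the single entry is titled "Refractory anastomotic bile leak leaks after orthotopic liver transplantation are associated with hepatic artery disease". Hepatic artery disease is mentioned nowhere else.
- *Background* introduces that source with the words "In a retrospective study of patients undergoing ERCP for post-OLT anastomotic bile leak at VUMC between 2009 and 2014". *Study timeline* projects recruitment from the same centre: "Assuming an annual OLT volume of 150 patients at VUMC".

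**The concern.** The plan takes its control rate from a cohort at its own centre but leaves aside the risk factor in that cohort's title, and that factor concerns the trial's primary outcome. With 32 per arm, and about 0.4 x 32 + 0.1 x 32 = 16 refractory leaks expected in all, a few more high-risk patients in one arm could move the crude comparison. The plan names no adjusted analysis, so any adjustment made after an imbalance was seen would be post hoc. If the unadjusted test were biased, or clearly weaker than an easy alternative, the primary result would be at stake.

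**Working it through.** **1. Reproduce the plan's figure.** Inputs from the statistical section: p1 = 0.40, p2 = 0.10, power 80%, alpha 0.05. Sidedness is not stated; two-sided is assumed. The mean rate is 0.25.

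n = [1.960 x sqrt(2 x 0.25 x 0.75) + 0.842 x sqrt(0.40 x 0.60 + 0.10 x 0.90)]² / 0.30²
= [1.960 x 0.6124 + 0.842 x 0.5745]² / 0.09
= (1.200 + 0.484)² / 0.09 = 31.5, so 32 per arm.

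This matches the plan. The sample size belongs to the uncorrected, unadjusted chi-square, which is the test named. Power at 32 per arm is 80.6% by the same formula and 82.8% by exact enumeration.

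**2. Is the unadjusted test valid when a prognostic factor is ignored?** Exact enumeration at 32 per arm gives a size of 5.2% at a common rate of 25%, and 5.6% at both 40% and 10%. In simulations with an ignored binary factor (prevalence 10-40%, odds ratio 2-8, common rate 25% or 40%) the size stayed between 4.9% and 5.6%. Randomisation protects the test whether or not the factor is used.

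**3. What would stratifying gain on average?** The documents give no prevalence, odds ratio or share of affected patients identified before ERCP, so all three are assumptions. With overall rates held at 40% and 10%, the unadjusted power is 82.8%. The change with a Mantel-Haenszel test stratified on the factor is:

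| Share of affected patients identified before ERCP | Odds ratio 1-3 | Odds ratio 5-10 |
|---|---|---|
| All | -1.3 to +0.7 points | +0.6 to +5.7 points |
| None | 0 | 0 |

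With half identified, the range over all odds ratios is -1.2 to +1.3 points. At an odds ratio of 3, about 80-85% must be identified just to break even, and at 10% prevalence break-even is never reached. A material gain needs both a strong link and near-complete knowledge beforehand.

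**4. What happens in imbalanced trials?** The arms differ by 5 or more affected patients in about 6%, 19% and 25% of trials at prevalence 10%, 25% and 40%. The excess is equally likely in either arm. With every affected patient identified:

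| Odds ratio | Crude power, excess in FCSEMS | Crude power, excess in plastic | Mean of the two | Stratified power, either direction |
|---|---|---|---|---|
| 3 | about 73% | about 91% | 82% | 79-82% |
| 5 | about 67% | about 94% | 80.5% | 80-84% |
| 10 | about 60% | about 97% | 78.5% | 82-88% |

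The higher crude power in the third column is produced by the imbalance and is no merit. But quoting only the unfavourable direction overstates the loss.

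Type I error follows the same pattern. In imbalanced trials the crude size at a 25% null is about 6-7%, 8% and 10-11% at odds ratios 3, 5 and 10. The remaining trials offset this. At 25% prevalence and odds ratio 5, for example, 0.19 x 8% = 1.5%, which leaves (5.2% - 1.5%) / 0.81 = 4.5% in the other trials and 5.2% overall.

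**5. Do the documents show that the factor is usable?** They do not.

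- *Eligibility* requires no vascular assessment, and no baseline variable is listed for collection.
- A title that reports an association does not say that the disease was known before the ERCP; it could have been found while a leak already refractory was being worked up.
- *Study intervention* randomises only high-grade leaks with wire access across them, and *Eligibility* excludes hepaticojejunostomy and prior percutaneous biliary intervention. *Background* does not say that the cohort was restricted in this way, so the association may not carry over unchanged.

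**The case for a change.** The strongest case for acting accepts that the test is valid and rests on fixing matters in advance. With about 16 events, a chance imbalance in a strong factor does distort that particular trial, and stratification largely repairs it: at an odds ratio of 10, with the excess in FCSEMS, power is about 60% crude and 82-87% stratified. If the investigators could choose between the two tests after seeing the data, type I error would be 5.5-7.2% at a 25% null and about 7.7% at a 40% null. A look-up in the centre's own cohort and one chart item would be cheap.

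Part of this stands. The factor comes from the plan's own evidence, and a pre-specified supportive stratified analysis would be reasonable. Three things keep it from being a correction. First, the plan names exactly one primary test, so it does not itself open a choice between two. Second, the repair fades when identification is incomplete: with half identified, the same odds ratio and direction give 69-71%. Third, whether stratification should be primary depends on facts outside the documents, and a look-up might well end with the chi-square kept. There is also a cost. The stents are visibly different and no blinding is described, so changing the primary test during the trial could attract the very post hoc criticism it was meant to prevent.

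**Conclusion.** The concern does not hold. The unadjusted chi-square is valid under randomisation (exact size 5.2-5.6% at common rates of 10%, 25% and 40%), it is the test for which 32 per arm was calculated, and it contradicts nothing else in the document. Not using hepatic artery disease changes no stated figure.

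The possible gain is -1.3 to +5.7 points of power with full identification before ERCP, about -1.2 to +1.3 points with half, and nothing with none. These ranges rest on an assumed prevalence of 10-40% and an assumed odds ratio of 1-10, the same in both arms; the documents support no narrower range. A supportive stratified analysis would leave the primary result as it is. Making it primary in a 64-patient trial is a trade-off on which experienced statisticians would differ. The plan needs no change on this point.
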